3.7 Post-Study Evaluation

The following tests and procedures should be performed, if possible, at the time a patient comes off study regardless of the reason for coming off study, unless the test or procedure has been performed in the past 6 weeks (2 weeks for physical examination and laboratory assessment).

- 3.7.1 HISTORY & PHYSICAL EXAMINATION (including a neurologic exam, performance status, and measurement of visible or palpable tumor lesions).
 - 3.7.2 Photographs of visible lesions (See Section 3.4.2)
 - 3.7.3 LABORATORY ASSESSMENT

Complete blood count, differential and platelet count, PT, and PTT. Electrolytes, creatinine, calcium, magnesium, phosphorus, SGPT, bilirubin. Urinalysis.

3.7.4 MRI Scan of the index lesions and any other progressing lesions using the protocol outlined in Appendix 1.

4.0 SUPPORTIVE CARE

GENERAL: Appropriate antibiotics, blood product support, antiemetics and general supportive care will be used as indicated.

HEMATOPOIETIC GROWTH FACTORS: Hematopoietic growth factors (e.g., EPO, G-CSF, GM-CSF) should **not** be administered except to those patients with either grade 4 neutropenia and blood culture positive septicemia, or grade 4 neutropenia of ≥7 days duration.

5.0 DATA COLLECTION AND EVALUATION

5.1 DATA COLLECTION

The POB, NCI will coordinate data collection and supply the data to the trial sponsor (CTEP) via the CDUS online system. Data will also be entered into the NCI Center for Cancer Research (CCR) C3D database. Documentation and date of IRB approval must be provided to CTEP and the POB, NCI prior to initial patient entry from each institution. The completed Eligibility Checklist and On-Study Form (Appendix 8 A/B) must be faxed to [name] at [contact] prior to patient entry onto the trial. The completed Tumor Progression Checklist and Crossover / Off-Study Form (Appendix 9A/B) must be faxed to [name] at the time a patient has documented tumor progression on treatment phase "A" and on treatment phase "B".

5.1.1 Case Report Forms

Case Report Forms have been developed by the POB. CRFs should be completed after each patient evaluation and submitted within 2 weeks of completion of each evaluation to:

Pediatric Oncology Branch, NCI c/o [name] [contact] [name] [name] Bethesda, MD 20892-1928

The following forms should be submitted to the POB:

ELIGIBILITY CHECKLIST AND BLINDED PATIENT ON STUDY FORM (APPENDIX 8 A/B): To be completed at study entry and forwarded to [name] [contact] (Phone, [contact])

PROGRESSION CHECKLIST AND BLINDED PATIENT CROSSOVER / OFF-STUDY FORM (Appendix 9A/B): To be completed and forwarded to [name] [contact] (Phone, [contact]) when a patient progresses on treatment phase "A" and "B".

Patient Diaries and Pill Count Case Report Form (Appendix 11A/B): Patients or their guardians will keep a diary to document the intake of each dose of R115777 or placebo and potential side effects (Appendix 11A). Each pharmacy will use the Pill Count Case Report Form (Appendix 11B). The completed diaries and Pill Count Case Report Forms will be forwarded to [name] after every three treatment cycles at [contact] (Phone, [contact]).

MRI STUDIES (Appendix 1): A copy of the MRI protocol used to obtain the baseline MRI study should be Faxed to [name] within 1 week of obtaining the MRI study. MRI studies should be submitted electronically or on CD or optical disk to the

NCI POB within 1 week of obtaining the study. The institutional radiology report for each study should be faxed to [name] within 1 week.

QOL ASSESSMENT (NIH IPI SCALE) FORMS: Patient and parent response forms should be photocopied after completion and copies sent to [name], Pediatric Oncology Branch, NCI, [contact], [name], Bethesda, MD 20892-1928 within 2 weeks of completion of the cycle of therapy. Any questions regarding the administration of the IPI Scale should be addressed to [name]. at [contact], e-mail: [contact].

LABORATORY STUDIES: Results of laboratory studies requested per protocol should be faxed to [name] within 1 week of performing the study.

Protocol violations should be directly reported to [name] ([contact], [contact], e-mail: [contact]).

Patients will be identified in all data collection forms and on photographs only by their initials and study number in an effort to maintain patient confidentiality. All patient documents, including informed consent and case report forms, will be kept in designated offices, in locked file cabinets with access only to personnel involved in the clinical trial. The NCI Center for Cancer Research (CCR) C3D electronic database is password protected and allow access only to persons directly involved in the clinical trial. All documents will be stored for at least 2 years after the drug has received marketing approval, or after the decision has been made not to market the drug.

5.2 RESPONSE CRITERIA

Response is assessed at the time that follow-up 3D-MRI scans are performed (prior to cycles 4, 7, 10, then q6 cycles). For the purpose of determining the level of response (complete, partial, minor, etc.) measurements from the follow-up scans are compared to the tumor size in the pretreatment MRI scan using 3D data analysis. Response determined using 3D-MRI volumetric analysis will be compared with 2D- and 1D-MRI measurements.

COMPLETE RESPONSE (CR): A complete resolution of all measurable or palpable soft tissue tumors for ≥ 4 weeks and no appearance of new lesions.

PARTIAL RESPONSE (PR): A \geq 50% reduction in the sum of the volume of all index lesions for \geq 4 weeks.

MINOR RESPONSE (MR): A \geq 25% but <50% reduction in the sum of the volume of all index lesions for \geq 4 weeks.

STABLE DISEASE (SD): A <20% increase, and < 25% decrease in the sum of the volume of all index lesions for ≥4 weeks.

PROGRESSIVE DISEASE (PD):

 A ≥ 20% increase in the volume (by 3D-MRI) of at least one of the index plexiform neurofibromas compared to the pretreatment volume measured prior to the start of the current treatment phase.

- The appearance of new discrete subcutaneous neurofibromas does not qualify for disease progression.
- Worsening of existing symptoms or the appearance of new symptoms that persist
 for more than 7 days and that are felt to be definitely related to the plexiform
 neurofibroma should be evaluated by repeating the MRI. Patients should not be
 classified as having progressive disease solely on the basis of new or increased
 symptoms without discussing the case with the protocol Principal Investigator.
- Patients with other evidence of disease progression than outlined above should also be discussed with the Principal Investigator.

5.3 TOXICITY CRITERIA

Toxicity will be graded according to the CTEP Expanded Common Toxicity Criteria, version 2. The Cancer Therapy Evaluation Program Common Toxicity Criteria (CTC) Version 2.0 will be used for toxicity assessment. A copy of the CTC version 2.0 can be downloaded from the CTEP home page (http://ctep.cancer.gov).

5.4 STATISTICAL CONSIDERATIONS

5.4.1 Subject Accrual

Subjects of both genders, from all racial and ethnic groups are eligible for this trial if they meet the criteria outlined in Section 2.1. To date, there is no information that suggests differences in drug metabolism or disease response among racial or ethnic groups or between the genders, indicating that results of the trial will be applicable to all groups. Most plexiform neurofibroma grow out of proportion to somatic growth for a period of time during childhood, but reach a plateau by the end of puberty. Efforts will be made to extend the accrual to a representative population, but in a phase II study with limited accrual, a balance must be struck between patient safety considerations and limitations on the number of individuals exposed to potentially toxic or ineffective treatments on the one hand and the need to explore gender, racial, and ethnic aspects of clinical research on the other. If differences in outcome that correlate to gender, age, racial, or ethnic identity are noted, accrual may be expanded or additional studies may be performed to investigate those differences more fully.

5.4.2 STATISTICS AND FEASIBILITY

The primary objective of the study is to determine whether R115777 ("drug") is able to increase the time to progression of patients who have NF1 with progressive plexiform neurofibromas. The study will be conducted as a crossover, two-arm randomized, double-blind, placebo controlled trial. After being randomized to drug or placebo, patients will be followed until progression. Once patients have progressed (documented by MRI), they will be crossed over to receive the placebo if they originally

received drug, and drug if they originally received placebo. Because the time until crossover is dependent on time until progression, this differs from a classic crossover study, in which patients are followed on both treatment arms for a predetermined fixed period of time, evaluated, given a wash-out period, and then followed identically on the other agent. As such, results from the first placebo vs. drug period will be used to determine sample size, and will constitute the primary endpoint of time to disease progression. The natural history of the growth rate and range of plexiform neurofibromas is not well known. In addition to the analysis of time to disease progression on the first treatment phase, a paired comparison of the first and second treatment phase (each patient will serve as his/her own control) will be performed using appropriate non parametric methods. This analysis will also help provide additional information on the differences in the natural history of NF1, and also address the effect of other variables, for example age differences, which may impact on the growth rate of plexiform neurofibromas.

Because the estimate of time to progression for patients eligible for this trial is approximately 6 months, it would be desirable to increase this time to 12 months. A one-tailed hypothesis will be used since it would only be considered interesting to see the improvement of drug compared to placebo. With 80% power and a one-tailed alpha=0.05, in order to detect a difference in median time to progression (during the first part of the trial) between the two arms of 6 vs. 12 months, 30 patients per arm are required (60 total) assuming 36 months of accrual and 12 months of additional follow-up following entry of the last patient. Kaplan-Meier analysis using log-rank statistics will be used to perform the required evaluation. We plan to replace patients who were diagnosed with a malignant peripheral nerve sheath tumor (MPNST) after enrolling on study, as these patients will not be evaluable for the primary outcome measure, which is time to progression of progressive plexiform neurofibromas. For this reason we will increase the accrual ceiling to 63 patients

Randomization of patients between the two study arms will be performed centrally by Orkand (See Section 3.1.1, 3.1.2). With more than one institution participating, it is expected that 20 patients per year can be entered onto the trial, with an expected accrual period of 3 years.

This trial will be monitored by the NCI/DCS Data Safety and Monitoring Board. Due to the projected accrual rate, it is expected that 3 interim evaluations and a final evaluation will take place at each of 4 consecutive annual meetings of the DSMB. Using the O'Brien-Fleming approach, if the p-values at the following evaluations are less than or equal to those tabled below, then the trial would be declared to have a statistically significant result; no further accrual would be required once such a determination has been made.

Evaluation #	Threshold p-Value (one-tailed)
1	0.00005

2	0.0039
3	0.0184
4 (FINAL)	0.0412

In addition, if, at any annual evaluation, a conditional power analysis indicates that there is a minimal chance of declaring a significant advantage to drug with the addition of the remaining planned patients based on results to date and the hypothesized results, then the DSMB may choose to close the study to further accrual.

Time to progression between the two study arms will be compared separately for the two periods of the cross-over study; initial treatment and second (crossover) treatment. Both comparisons will be reported in order to describe the effect of drug on this endpoint. In addition, because each patient will have received both placebo and drug, comparisons of time to progression can be undertaken between both treatment conditions, employing methodology for paired subject data in order to further interpret the findings.

The quality of life of patients treated with R115777 and placebo on this study will be assessed using the National Institutes of Health (NIH) Impact of Pediatric Illness (IPI) Scale (Section 1.2.8), and scores of patients will be compared using the paired t-test.

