2.0 ENROLLMENT PROCEDURES

2.1 ELIGIBILITY CRITERIA

- 2.1.1 INCLUSION CRITERIA
 - 2.1.1.1 Age: ≥3 years and ≤25 years of age
- 2.1.1.2 Diagnosis: Patients with NF1 and progressive plexiform neurofibromas that have the potential to cause significant morbidity, such as (but not limited to) head and neck lesions that could compromise the airway or great vessels, brachial or lumbar plexus lesions that could cause nerve compression and loss of function, lesions that could result in major deformity (e.g., orbital lesions), lesions of the extremity that cause limb hypertrophy or loss of function, and painful lesions. Histologic confirmation of tumor is not necessary in the presence of consistent clinical and radiographic findings, but should be considered if malignant degeneration of a plexiform neurofibroma is clinically suspected. In addition to plexiform neurofibroma(s), all study subjects must have at least one other diagnostic criteria for NF1 listed below (NIH Consensus Conference[9]):
 - 1. Six or more café-au-lait spots (≥0.5 cm in prepubertal subjects or ≥1.5 cm in postpubertal subjects)
 - 2. Freckling in the axilla or groin
 - 3. Optic glioma
 - 4. Two or more Lisch nodules
 - 5. A distinctive bony lesion (dysplasia of the sphenoid bone or dysplasia or thinning of long bone cortex)
 - 6. A first degree relative with NF1

In this study a plexiform neurofibroma is defined as a neurofibroma that has grown along the length of a nerve and may involve multiple fascicles and branches. A spinal plexiform neurofibroma involves two or more levels with connection between the levels or extending laterally along the nerve.

2.1.1.3 Measurable disease: Patients must have measurable plexiform neurofibroma(s). For the purpose of this study a measurable lesion will be defined as a

lesion of at least 3 cm measured in one dimension. There must be evidence of recurrent or progressive disease as documented by an increase in size or the presence of new plexiform neurofibromas on MRI. Progression at the time of study entry is defined as:

- A measurable increase of the plexiform neurofibroma (≥ 20% increase in the volume, or a ≥ 13% increase in the product of the two longest perpendicular diameters, or a ≥ 6% increase in the longest diameter) over the last two consecutive scans (MRI or CT), or over the time period of approximately one year prior to evaluation for this study.

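### The 6-month control median has no stated source, and with no event target and almost no slack in expected events the 80% power depends on it

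*Combined protocol and SAP*

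**What the plan says.** Section 5.4.2 takes the control median from one statement: "Because the estimate of time to progression for patients eligible for this trial is approximately 6 months". It aims to double this to 12 months and sizes the first-phase log-rank comparison "With 80% power and a one-tailed alpha=0.05", arriving at 30 patients per arm, "assuming 36 months of accrual and 12 months of additional follow-up following entry of the last patient". Three interim evaluations and a final one are expected at four consecutive annual DSMB meetings, with a final one-tailed threshold of 0.0412. No number of events is given for any look. The accrual ceiling of 63 covers only replacement of patients found to have a malignant peripheral nerve sheath tumour.

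On growth, the same section says: "The natural history of the growth rate and range of plexiform neurofibromas is not well known". Section 1.2.8 reports that the natural-history study has no results yet, and that some lesions stop growing after an active period. Section 5.4.1 says most lesions "reach a plateau by the end of puberty"; section 2.1.1.1 admits patients up to age 25.

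Section 2.1.1.3 requires growth of at least 20% in volume (or the 2D or 1D equivalent), either between the last two scans or "over the time period of approximately one year prior to evaluation for this study". It also admits incompletely resected tumours after surgery. Section 3.1.5 defines on-study progression as at least 20% volume growth in any one index lesion.

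**The concern.** Log-rank power is governed by the number of events, and the number of events in a calendar-timed analysis is governed by the control median. Here that median is one unsourced figure, in a disease whose growth the protocol itself calls unpredictable.

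The entry threshold and the endpoint are the same 20% volume increase, so the entry rule is the only place in the documents where the 6-month figure can be checked. It does not settle the matter. If control tumours progress more slowly than assumed, the analysis at month 48 has fewer events than the stated power requires, even if the drug doubles the time to progression exactly as hoped. Nothing in section 5.4.2 would correct this: it has no event target, no rule to extend follow-up and no check of the pooled event rate. The conditional-power provision can only close accrual. The possible expansion of accrual in section 5.4.1 concerns differences by gender, age, race or ethnicity. At stake is an inconclusive result from a placebo-controlled trial in children.

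**Working it through.** **Inputs from section 5.4.2.** Medians 6 and 12 months (hazard ratio 0.5 if exponential); one-tailed 0.05; 80% power; 30 per arm; accrual A = 36 months; follow-up after last entry F = 12 months; final threshold 0.0412. **Assumed here:** exponential times, uniform accrual, no dropout.

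**1. The plan's own figure.**
- Events needed (Schoenfeld): d = 4(1.645 + 0.842)² / (ln 0.5)² = 51.5.
- Probability of an event by month 48, with λ = ln 2 / median: p = 1 − [exp(−λF) − exp(−λ(A+F))] / (λA). This is 0.941 on placebo and 0.790 on drug.
- Expected events: 30 × (0.941 + 0.790) = 51.9.
- Power = Φ(0.693·√d / 2 − z). With d = 51.9: 80% at z = 1.645 (0.05) and 78% at z = 1.737 (0.0412).

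The stated 60 patients therefore reproduce. The margin is 51.9 − 51.5 = 0.4 events.

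**2. What the entry rule implies.** At constant growth, a patient who gained 20% over a year reaches the endpoint in about 12 months. A patient reaching it in 6 months grows 1.2² − 1 = 44% a year. The rule is a floor, so it admits both. A 6-month median requires half the controls to grow at 44% a year or faster; the documents neither show nor exclude this.

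**3. Longer control medians, hazard ratio kept at 0.5, analysis at month 48.** The 9- and 12-month rows are an assumed range, not a forecast.

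| Medians (months) | Expected events | Power, 0.05 | Power, 0.0412 |
|---|---|---|---|
| 6 vs 12 | 51.9 | 80% | 78% |
| 9 vs 18 | 45.7 | 76% | 73% |
| 12 vs 24 | 40.5 | 71% | 68% |

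For the last row, 30 × (0.790 + 0.560) = 40.5.

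A simulation of the log-rank test with all four tabled thresholds (2,000 runs) gives about 78% at a 6-month control median and 68% at 12 months.

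**4. Other calls on the missing reserve, with 6 vs 12 months kept.** Reading progression only on the MRI schedule gives about 50 events and 76% power (simulated, tabled thresholds). An assumed 10% yearly dropout gives 48.1 events and 78% at one-tailed 0.05.

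**5. What an event trigger delivers.**
- 52 events give 80% at 0.05 and 78% at 0.0412. For 80% at 0.0412, d = 4(1.737 + 0.842)² / (ln 0.5)², about 55 events.
- 52 expected events arrive about 12 months after last entry at 6 vs 12, about 24 months at 9 vs 18, and about 37 months at 12 vs 24.
- With a cap at 24 months after last entry, 12 vs 24 gives p = 0.895 and 0.689, so 30 × 1.584 = 47.5 events and 77% power at 0.05 (74% at 0.0412).

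**The case against.** A reader might infer that the 6-month median contradicts the entry rule. It does not. The rule is a minimum, its one-year window is one of two alternatives, and the two-scan window has no stated interval. Progression in any one of up to three index lesions also shortens the time to the endpoint. For a patient admitted on volume growth over one year, 12 months is the slowest case at constant growth, not the typical one.

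A reader might also infer that a shortfall is likely. The documents give no growth-rate distribution, so that cannot be shown. The plateau remark describes lesions in general, whereas entrants are selected for recent progression. Against that, the protocol says growth may stop, and it admits residual tumours after surgery, so slower growth is possible but of unknown extent.

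The four annual evaluations and 12 months of follow-up are worded as expectations and assumptions, not as a fixed data cutoff. That stands; the accurate criticism is that no event target is stated.

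The loss is modest for small departures: 77% at a control median of 8 months. An event trigger also does not rescue a smaller effect. If the drug adds 6 months to a 12-month control median (12 vs 18), power is 38% at month 48 and only about 43% at 52 events. That loss comes mainly from the hazard ratio of 0.67, so it is no argument for the trigger.

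Finally, 52 of 60 patients is 87%. If some lesions stay static, the target may never be reached and a cap would govern. This is why a cap belongs in the proposal.

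**Conclusion.** The point holds as a planning weakness, not as an error of arithmetic. N = 60 is right at a fixed one-tailed 0.05 under the stated assumptions. The control median behind it is unsourced, the entry rule allows it without supporting it, and there is neither a reserve of events nor an event target. With a hazard ratio of 0.5, every control median above 6 months lowers power at month 48: by about 4 percentage points at 9 months and 9 at 12 months.

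These sizes rest on exponential times, uniform 36-month accrual, no dropout and assumed control medians. How far the true median lies from 6 months cannot be told from the documents. The change is worth making because it protects the stated power at low cost.

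**What to change.** In section 5.4.2:

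- State the source of the 6-month estimate, or say that it is a judgement.
- Trigger the final analysis at about 52 first-phase progressions or at a stated maximum follow-up, for example 24 months after last entry, whichever comes first.
- Time the DSMB looks by event fraction instead of by annual meeting.
- State that 52 events give about 78% power at the tabled 0.0412, and that about 55 are needed for 80%.
- Report power at control medians of 9 and 12 months beside the 6-month figure, labelled as an assumed sensitivity range.

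**Cost.** Wording and no extra patients. Sections 3.1.3 and 5.4.2 already keep patients on therapy until an off-study criterion is met and follow them to progression, so the trigger changes when the data are read. The price is a readout up to about 12 months later under the example cap, with blinded treatment and MRI follow-up running on for patients who have not progressed. If the medians are 6 and 12 months, little or no delay is expected. At 12 vs 24 months the cap would bind, at about 47.5 events and 77% power (one-tailed 0.05) instead of 40.5 events and 71%.

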3.1.4 MONITORING TIME TO PROGRESSION AND RESPONSE

This phase II trial is designed to determine the time to tumor progression and response rate with R115777 in patients with NF1 and progressive plexiform neurofibromas. The primary endpoint will be time to progression. Each patient will undergo MRI imaging of all known disease prior to entry on study. At the time of study entry one to three progressing plexiform neurofibroma(s) will be identified as index lesion(s), and followed for progression and response using 1D-, 2D-, and 3D-MRI. Results obtained with 1D-MRI and 3D-MRI analysis will be compared to conventional 2D-MRI analysis for their ease and reproducibility. The imaging protocol outlined in Appendix 1 will be used each time MRI scans are performed to assess response to R115777. MRI scans are performed prior to cycles 1, 4, 7, 10, and then after every 6 cycles on each study phase. If a patient is removed from a study phase because of clinical evidence of disease progression, the MRI scans should be repeated if they had not been performed within the past 4 weeks.

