3.1.5 Definition of Tumor Progression

- A ≥ 20% increase in the volume (by 3D-MRI) of at least one of the index plexiform neurofibromas compared to the pretreatment volume measured prior to the start of the current treatment phase.
- Appearance of new discrete dermal neurofibroma(s) does not qualify for disease progression.
- Worsening of existing symptoms or the appearance of new symptoms that persist for more than 7 days and that are felt to be definitely related to plexiform neurofibroma should be evaluated by repeating the MRI. Patients should not be classified as having progressive disease solely on the basis of new or increased symptoms without discussing the case with the protocol Principal Investigator.
- Patients with other evidence of disease progression than outlined above should also be discussed with the Principal Investigator.

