3.4.4 RADIOGRAPHIC EVALUATION: Evaluate the index lesions by MRI prior to cycle 1 on treatment phase "A", and prior to cycle 4, 7, 10, and then after every 6 cycles on each treatment phase ("A", "B"). The protocol outlined in Appendix 1 will be used each

time MRI examinations are performed to assess progression or response to R115777 or placebo. In patients with clinical suspicion of disease progression MRI analysis should be performed earlier using the protocol outlined in Appendix 1. At the time of disease progression on treatment phase "A", if possible, a MRI scan of all known measurable plexiform neurofibromas in addition to the index lesions should be performed, in order to have a new baseline prior to treatment phase "B" (Appendix 1).

- 3.4.5 OPHTHALMOLOGIC EVALUATION: Prior to or within the first three days of starting treatment phase "A", and prior to or within the first 3 weeks of starting treatment phase "B". Exam should include visual fields if the patient is able to cooperate with the exam and examination of the lens for opacifications.
- 3.4.6 TISSUE PROCUREMENT: In patients with easily accessible discrete neurofibromas or superficial plexiform neurofibromas, who consent to the procedure, biopsies will be performed prior to the first dose of treatment on phase "A", and if feasible at one steady state time point on each treatment phase ("A", "B") (between day 15-21 on cycle #1) of treatment. In addition, attempts will be made to obtain tumor specimens from any patients requiring surgery for complications of their tumors or for unrelated medical problems. Peripheral blood mononuclear cells for FPTase assay (Section 3.4.7, appendix 5) should be obtained at the same time as biopsy whenever possible. As this is an invasive procedure, patients may refuse biopsy and still be eligible for the study.

Two kits will be supplied for handling and shipping of tumor specimens. To obtain the kits, please call [name] [contact]. Kits will be sent by FedEx to arrive several days prior to the surgical procedure. Included in the kits will be all media and tubes needed for shipment. Procedures for tissue handling and shipment are provided in Appendices 3 and 4, respectively.

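### The 80% power in Section 5.4.2 is a one-look, exact-time figure; the plan's four looks give about 78%, and about 76% with the MRI schedule if 6 and 12 months are true medians

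*Combined protocol and SAP*

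**What the plan says.** Section 5.4.2 sets the power statement ("With 80% power and a one-tailed alpha=0.05, in order to detect a difference in median time to progression") for medians of 6 and 12 months. It requires 30 patients per arm with 36 months of accrual and 12 months of further follow-up. On the control median it says that "the estimate of time to progression for patients eligible for this trial is approximately 6 months". The primary test is given as "Kaplan-Meier analysis using log-rank statistics will be used to perform the required evaluation".

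The same section then says that "it is expected that 3 interim evaluations and a final evaluation will take place at each of 4 consecutive annual meetings of the DSMB". It tables one-tailed O'Brien-Fleming thresholds of 0.00005, 0.0039, 0.0184 and 0.0412.

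Progression is an imaging finding. Section 3.1.5 requires a 20% or greater "increase in the volume (by 3D-MRI) of at least one of the index plexiform neurofibromas compared to the pretreatment volume", and Section 5.4.2 ties crossover to it: "Once patients have progressed (documented by MRI), they will be crossed over to receive the placebo" or the drug, according to the first assignment. On timing, Section 3.1.4 says "MRI scans are performed prior to cycles 1, 4, 7, 10, and then after every 6 cycles on each study phase". Section 3.4.4 adds an exception: "In patients with clinical suspicion of disease progression MRI analysis should be performed earlier using the protocol outlined in Appendix 1".

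Appendix 9B records Phase A progression and crossover in one shared date field.

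**The concern.** The sample size is derived from one alpha of 0.05 and continuous medians. The plan then spends alpha over four looks and observes the endpoint only when a scan is done. Section 5.4.2 states no allowance for either feature, nor whether 6 and 12 months are the times at which tumours truly cross the threshold or the times at which MRI would show it. The stated power is the figure a reader will use to interpret a negative result, so it should describe the design that will be run.

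A smaller gap sits beside it. Sections 3.1.5 and 5.2 define what progression is, but no sentence says which date enters the primary analysis. The shared field in Appendix 9B leaves that open, since Section 3.1.1 puts a two-week washout between the phases.

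**Working it through.** **Inputs from the documents.** 30 per arm; medians 6 and 12 months; one-tailed 0.05; accrual A = 36 and follow-up F = 12 months; four looks with the tabled thresholds (Section 5.4.2). Scans before cycles 4, 7 and 10, then every 6 cycles (Section 3.1.4); 28-day cycles (Section 3.1.3).

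**Assumptions.** Exponential times, uniform accrual, no dropout, looks at months 12, 24, 36 and 48. The documents state none of these exactly.

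**1. Reproduce the stated figure.** Hazard ratio = 6/12 = 0.5.

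- Events needed (Schoenfeld): 4(1.645 + 0.842)²/(ln 2)² = 51.5, so 52.
- Probability of an event by month 48: 1 − [exp(−λF) − exp(−λ(A+F))]/(λA).
- Placebo, λ = ln 2/6: 1 − (0.25 − 0.0039)/4.159 = 0.941.
- Drug, λ = ln 2/12: 1 − (0.5 − 0.0625)/2.079 = 0.790.
- Expected events: 30 × (0.941 + 0.790) = 51.9.
- Power: Φ(√51.9 × ln 2/2 − 1.645) = Φ(0.852) = 80.3%. Simulated: 79.1 to 79.6%.

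The plan's figure is therefore a one-look, exact-time calculation.

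**2. Add the four looks.** Expected events at the looks are 7.4, 22.4, 40.3 and 51.9, or information fractions 0.14, 0.43, 0.78 and 1. The final threshold alone gives Φ(2.497 − 1.737) = 77.6%. The full four-look boundary gives 78.5% by a Brownian-motion calculation and 77.5 to 77.9% in simulated log-rank tests.

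**3. Add the MRI schedule, with 6 and 12 as true medians.** Scans fall at 84, 168, 252, 420 and 588 days. Divided by 30.44, these are 2.8, 5.5, 8.3, 13.8 and 19.3 months, then every 5.5 months. Each progression is dated at the next scheduled scan, and patients without progression are censored at their last scan. Expected events at month 48 fall from 51.9 to 50.0.

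| Case (60 patients, true medians 6 and 12) | One look at 0.05 | Four looks |
|---|---|---|
| Exact times | 79.1 to 79.6% | 77.5 to 77.9% |
| Scheduled MRIs only | 77.5 to 77.7% | 75.4 to 75.8% |

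Ranges are over repeated simulations of 15,000 to 100,000 trials. If 25% of progressions are found by unscheduled scans one week after onset (an assumption), the four-look figure is 75.4%; at 50% it is 75.5%.

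**4. Read 6 and 12 as MRI-detected medians.** The true medians must then be earlier, but the documents do not say by how much in each arm. With four looks and scans:

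| Assumed true medians | Hazard ratio | Power |
|---|---|---|
| 4.62 and 9.24 (half a scan gap: 6 − 1.38, 12 − 2.76) | 0.50 | 77.3 to 77.6% |
| 5.0 and 10.5 | 0.476 | 81.5% |
| 4.6 and 9.9 | 0.465 | 84.3% |
| 4.62 and 10.62 (equal delay of 1.38) | 0.435 | 88.6 to 89.3% |

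The result turns on the hazard ratio, which the plan does not fix on this reading.

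**5. Type I error with four looks.** About 0.046 by the Brownian-motion calculation; 0.048 to 0.051 simulated, with or without the scan schedule.

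**6. The progression date.** Section 5.2 assesses response, including progressive disease, when the follow-up scans are done. Section 5.4.2 requires MRI documentation before crossover, and Section 5.5.5 makes central volumetric MRI the basis of the endpoint. Section 7.2 requires the Appendix 9A/B forms before a patient can cross over, so their date would ordinarily precede Phase B dosing. All of this points to the MRI, but no sentence says so.

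**The case against.** The strongest objection is that the loss is too small to matter. The looks alone cost about 2 points. The plan calls its control median approximate and says the natural history is not well known; a placebo median of 6.25 instead of 6 months, with the drug at 12, would bring even the one-look, exact-time power to about 75%. This stands, and it is why the point asks for a restatement and not for more patients.

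A reader might infer that the design misses 80% however the medians are read. The documents do not support that. On the detected reading, a shortfall appears only if the hazard ratio is held at 0.5, which is an added assumption; equally compatible assumptions give more than 80%.

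A reader might also infer that dating events at scans invalidates the log-rank test or calls for an interval-censored analysis. Both arms are scanned on one schedule and type I error stays near 0.05, so no error in the plan requires it.

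Finally, the shared date in Appendix 9B could be read as adding the washout to the primary endpoint. The sections set out in step 6 make that unlikely; what is missing is one clarifying sentence.

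**Conclusion.** The point holds and is minor. The stated 80% describes a single test on exact times. Under the plan's four looks it is about 78%, a loss of about 2 points. With the MRI schedule as well it is about 75 to 76%, a loss of about 4 points, provided that 6 and 12 months are true medians. If they are MRI-detected medians, power is about 77% at a hazard ratio of 0.5 and higher if the effect is stronger, so no shortfall is shown.

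The accrual ceiling of 63 does not recover the loss, because the extra places replace patients found to have a malignant peripheral nerve sheath tumour. The sample size need not change.

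The figures rest on the assumptions listed in the working. The optional conditional-power stop has no stated threshold and is not modelled; it could only lower power.

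**What to change.** In Section 5.4.2:

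1. State that 80% is the power of the fixed design with one test at one-tailed 0.05 and exact progression times.
2. Add that 60 patients give about 78% under the four planned looks, and about 76% under the four looks with the MRI schedule if 6 and 12 months are true medians.
3. Say whether 6 and 12 months are true or MRI-detected medians. If detected, give the underlying hazard ratio assumed and the power that follows from it.
4. State that time to progression is dated at the MRI that documents it, so that the shared date in Appendix 9B cannot be read otherwise.

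The log-rank test, thresholds and sample size stay as they are. The cost is a few sentences and a slightly lower stated power; no extra patients, scans, follow-up or forms are needed.
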